3 STUDY DESIGN

3.1 General Description

The target population is adults who use opioids recreationally. The design of the study is a 2-arm fixed-sequence, double-blind study performed at a single site. The IP being investigated is AZD4041 alone and in combination with morphine.

3.2 Treatments

The active and placebo treatment groups are presented as two sequences: Sequence 1 and Sequence 2. In Sequence 1, subjects are administered [CC1] of morphine on Day 1, then [CC1] of AZD4041 on Days 2 through 14, then both [CC1] of morphine and [CC1] of AZD4041 on Day 15. Sequence 2 is similar to Sequence 1, but with AZD4041 replaced with a placebo. Sequence 2 subjects receive [CC1] of morphine on Day 1, then placebo on Days 2 through 14, then both [CC1] of morphine and placebo on Day 15.

3.3 Study Procedures

For complete details on the study assessments to be performed for each study period, refer to [APPENDIX A](#).

3.4 Randomization and Unblinding Procedures

Subjects will be randomized into treatments as Sequence 1 or Sequence 2, as described in section 3.2. Sequence 1 will include 28 subjects total and Sequence 2 will include 16 subjects total. The total 44 subjects will be assigned into 6 Blocks, with Block 1 including 4 subjects (Sequence 1 to Sequence 2, 1:1), Blocks 2 through 5 including 8 subjects each (Sequence 1 to Sequence 2, 5:3), and Block 6 includes 8 subjects (Sequence 1 to Sequence 2, 3:1). Replacements may be made if subjects drop out of the study before completion.

The randomization code must not be broken except in emergency situations where the identification of a subject's study treatment is required by an Investigator for further treatment to the subject or to complete a SAE report. Randomization information will be held by designated individual(s). The date and reason for breaking the blind must be recorded.

Unblinding of the data will occur after database lock except in cases of emergency.

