## 3. STUDY DESIGN

#### **3.1. Overall Study Design**

This is a Phase 1, randomized, double-blind, placebo-controlled, 2 fixed sequences, multiple dose study in healthy male and/or female recreational opioid users.

This study will consist of 3 phases: Screening and Qualification, Treatment phase, and Follow-up (see Figure 3-1).

After a Screening period of up to 27 days (Day -30 to Day -3), eligible subjects will be admitted to the clinical research unit (CRU) on Day -2. Subjects will be randomized to 1 of 2 fixed treatment sequences (28 subjects in Sequence 1, and 16 subjects in Sequence 2) on Day -1.

Subjects will be required to present a negative urine drug and alcohol screen upon admission on Day-2, except for tetrahydrocannabinol (THC). If THC is positive at admission, a cannabis intoxication evaluation will be done by an Investigator, and subjects may be permitted to continue in the study at the discretion of an Investigator. Subjects will then undergo a naloxone challenge where an initial 0.2 mg intravenous (IV) dose of naloxone hydrochloride (HCl) will be administered. The subject will be observed for signs or symptoms of opioid withdrawal. If there is no evidence of withdrawal within 1 minute (as assessed by a Clinical Opioid Withdrawal Scale [COWS] score of <5), an additional 0.6 mg IV dose of naloxone HCl will be given, and the subject will be observed for signs and symptoms of withdrawal for 5 minutes (as assessed by COWS). Subjects who present symptoms of withdrawal during the qualification process will be excluded from the study and will not be eligible to enter the Treatment phase.

In total, subjects will be confined to the CRU for approximately 20 days from Day -2 to Day 18 (until approximately 72 hours following the last study drug administration).

On Day 1, subjects will receive a single CCI IV dose of morphine. From Day 2 to Day 15, subjects will receive a CCI oral dose of AZD4041 or placebo once daily for 14 consecutive days. On the morning of Day 15, the CCI oral dose of AZD4041 or placebo will be combined with a single CCI IV dose of morphine.

In order to limit the number of subjects being treated with investigational product (IP) on any single day, eligible subjects should be assigned to different subgroups. Subgroup sizes should be limited to no more than 8 subjects. Dosing of subgroups should be staggered to occur on different days, with at least 2 days between the start of dosing for sequential subgroups.

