(predose average from Days 2 to 15), and postdose average on Day 15 will also be summarized by treatment using descriptive statistics and inferential analysis.

For EtCO2, SpO2, and respiratory rate the following figures will be generated:

- Mean (± SD) treatment by time point for Day 1 Morphine alone matched to Day 15 Morphine + AZD4041
- Mean (± SD) treatment by time point for Day 1 Morphine alone matched to Day 15 Morphine + Placebo
- Mean (± SD) treatment by time point for Days 2-15 predose AZD4041 vs. Days 2-15 predose Placebo
- 4) Boxplot for  $E_{max}$  Day 1 Morphine alone matched to Day 15 Morphine + AZD4041
- 5) Boxplot for  $E_{max}$  Day 1 Morphine alone matched to Day 15 Morphine + Placebo
- 6) Boxplot for Emax Day 15 Morphine + AZD4041 vs. Day 15 Morphine + Placebo

For all inferential analysis on  $EtCO_2$ ,  $SpO_2$ , and respiratory rate, mixed-effects models will be used for  $E_{max}$  and averaged measures. The models will include treatment as a fixed effect, and baseline as a covariate. Homogeneity of treatment variances will be explored to determine if subject may be considered a random effect.

For maximum postdose increase in  $EtCO_2$  ( $E_{max (postdose - predose)}$ ), maximum postdose reduction in  $SpO_2$  ( $E_{max (predose - postdose)}$ ), and maximum postdose decrease in respiratory rate ( $E_{max (predose - postdose)}$ ), the following contrasts will be explored in the mixed-effects models:

- 1) E: Morphine + AZD4041 (Day 15) vs A: Morphine alone (Day 1)
- 2) F: Morphine + Placebo (Day 15) vs B: Morphine alone (Day 1)
- 3) E: Morphine + AZD4041 (Day 15) vs F: Morphine + Placebo (Day 15)

For EtCO2, SpO2, and respiratory rate averages (predose average from Days 2 to 15), and postdose average on Day 15, the following contrasts will be explored in the mixed-effects models:

- 1) E (postdose): Morphine + AZD4041 (postdose average Day 15) vs C + E (predose): AZD40401 (predose average Days 2-15)
- 2) C + E (predose): Morphine + AZD4041 (predose average Days 2-15) vs D + F (predose): Morphine + Placebo (predose average Days 2-15)

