For EtCO₂, SpO₂, and respiratory rate the following figures will be generated:

- 1) Sequence 1: Mean (\pm SD) treatment by time point for Day 1 Morphine alone matched to Day 15 Morphine + AZD4041
- 2) Sequence 2: Mean (\pm SD) treatment by time point for Day 1 Morphine alone matched to Day 15 Morphine + Placebo
- 3) Mean (\pm SD) treatment by time point for Days 2-15 predose AZD4041 vs. Days 2-15 predose Placebo
- 4) Boxplot for E_{max} Day 1 Morphine alone matched to Day 15 Morphine + AZD4041
- 5) Boxplot for E_{max} Day 1 Morphine alone matched to Day 15 Morphine + Placebo
- 6) Boxplot for E_{max} Day 15 Morphine + AZD4041 vs. Day 15 Morphine + Placebo

For all inferential analysis on EtCO₂, SpO₂, and respiratory rate, mixed-effects models will be used for E_{max} and averaged measures. The models will include sequence, time (as a ordered factor variable), and the sequence-by-time interaction as fixed effects and baseline as a covariate, with 95% confidence intervals reported along with p-values. Homogeneity of treatment variances will be explored to determine if subject may be considered a random effect. The covariance structure for the mixed models will be heterogeneous compound symmetry. If the heterogeneous compound symmetry model does not converge, then a compound symmetry structure will be used and a footnote will be added to identify the results as using a different covariance structure than usual. The kenwood-roger adjustment for the degrees of freedom will be used when calculating p-values due to the small sample size.

The maximum postdose decrease in respiratory rate (E_{max (predose - postdose)}) is the primary criterion. In addition to the primary criterion, maximum postdose reduction in SpO₂ (E_{max (predose - postdose)}) and The maximum postdose increase in EtCO₂ (E_{max (postdose - predose)}) will have the following contrasts calculated in the mixed-effects models:

- 1) Morphine + AZD4041 (Day 15) vs Morphine alone (Day 1) [Sequence 1]
- 2) Morphine + Placebo (Day 15) vs Morphine alone (Day 1) [Sequence 2]
- 3) Morphine + AZD4041 (Day 15) vs Morphine + Placebo (Day 15) [Sequence 1 vs Sequence 2]

For EtCO₂, SpO₂, and respiratory rate averages (predose average from Days 2 to 15), and postdose average on Day 15, the following contrasts will be explored in the mixed-effects models:

- 1) (postdose): Morphine + AZD4041 (postdose average Day 15) vs (predose): AZD40401 (predose average Days 2-15)

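### Allocation ratio varies by randomisation block, but block is in none of the respiratory models: a small, conditional weakness in the between-sequence contrasts that is cheap to remove

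*SAP*

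**What the plan says.** SAP 3.4 sets the totals ("Sequence 1 will include 28 subjects total and Sequence 2 will include 16 subjects total") and splits the 44 subjects into six blocks. The first is small and balanced ("with Block 1 including 4 subjects (Sequence 1 to Sequence 2, 1:1"), the middle four share one ratio ("Blocks 2 through 5 including 8 subjects each (Sequence 1 to Sequence 2, 5:3"), and the last leans further towards AZD4041 ("Block 6 includes 8 subjects (Sequence 1 to Sequence 2, 3:1"). It also allows replacements, without saying which block a replacement joins.

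For the analysis, SAP 9.1 states: "The models will include sequence, time (as a ordered factor variable), and the sequence-by-time interaction as fixed effects and baseline as a covariate". Protocol 8.3.2.1 is sparser: "The models will include treatment as a fixed effect, and baseline as a covariate". The SAP's covariance statement is "The covariance structure for the mixed models will be heterogeneous compound symmetry", which describes correlation between measurements and names no block component. Neither document has a block or dosing-subgroup term, or a sensitivity analysis for one.

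Protocol 3.1 doses subjects in staggered subgroups and says "Subgroup sizes should be limited to no more than 8 subjects". Blocks of 4 and 8 fit under that cap, but neither document says that a block is a dosing subgroup.

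**The concern.** With one ratio in every block, leaving block out would not bias the arm comparison. Here the ratio changes, so block and sequence are associated by design: Block 6 holds 6 of 28 AZD4041 subjects but only 2 of 16 placebo subjects. Anything that makes late subjects respond differently to morphine then enters the between-sequence comparison in part. Staggered dosing and interventions chosen at the investigator's discretion (Protocol 6.1.15) make such differences plausible.

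Two comparisons in SAP 9.1 are exposed. One is the third Emax contrast, AZD4041 against placebo on Day 15. The other is the between-sequence contrast on predose averages over Days 2 to 15. The first matters because Day 15 against Day 1 within Sequence 1 cannot by itself separate an AZD4041 effect from a period or repeat-morphine effect; the placebo arm is there for that. Block variance left in the residual also widens the interval, and in a study looking for respiratory harm an over-wide interval makes harm harder to see.

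**Working it through.** **Reproducing the plan's counts.** Sequence 1: 2 + 4×5 + 6 = 28. Sequence 2: 2 + 4×3 + 2 = 16. Total 44. These match SAP 3.4. There is no power calculation to reproduce (SAP 3.5, Protocol 8.5).

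**How much of each block's effect enters the contrast.** Without block in the model, the between-sequence difference contains each block's effect with weight n1/28 − n2/16, where n1 and n2 are that block's counts in Sequences 1 and 2.

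| Block | n1 : n2 | Weight |
|---|---|---|
| 1 | 2 : 2 | 2/28 − 2/16 = −0.054 |
| 2 to 5 (each) | 5 : 3 | 5/28 − 3/16 = −0.009 |
| 6 | 6 : 2 | 6/28 − 2/16 = +0.089 |

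The weights sum to zero.

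**Standard errors, in units of the residual SD.**
- Without block: √(1/28 + 1/16) = √0.0982 = 0.313.
- With fixed block: 1/√Σ[n1·n2/(n1 + n2)] = 1/√(1 + 4×1.875 + 1.5) = 1/√10 = 0.316, which is 0.9% larger.

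**Bias under assumed block effects.** The documents give no block effect, so these shifts are assumptions.
- Block 6 shifted by 1 SD: 0.089 SD; 0.089/0.313 = 0.28 SE. For scale, with the larger EtCO2 SD in Protocol 6.1.9 (3.88 mmHg, a baseline SD and not an Emax SD), this is 0.089 × 3.88 = 0.35 mmHg.
- Linear drift of 1 SD from first to last block: 0.071 SD, or 0.23 SE.
- Block 1 at −1 SD and Block 6 at +1 SD: 0.054 + 0.089 = 0.143 SD, or 0.46 SE.

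With fixed block in the model, the bias is zero in each case.

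**Interval coverage.** Simulation of 40,000 trials per scenario: a linear model on one Day 15 value per subject, 28 against 16, with no baseline covariate and no dropout. This is simpler than the planned mixed model. The block intraclass correlation (ICC) is assumed.

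| Block ICC | Coverage without block | Half-width without block (SD) | Coverage with fixed block | Half-width with fixed block (SD) |
|---|---|---|---|---|
| 0 | 94.9% | 0.628 | 94.9% | 0.636 |
| 0.10 | 95.9% | 0.658 | 95.0% | 0.636 |
| 0.20 | 96.4% | 0.692 | 94.9% | 0.636 |
| 0.30 | 97.3% | 0.734 | 95.1% | 0.636 |

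With a fixed 1 SD shift in Block 6, coverage without block is 95.7%. In every scenario run, the interval without block is correct or too wide; none is materially too narrow. At ICC 0.20 the squared width ratio is (0.692/0.636)² = 1.18, equivalent to giving up about 1 − 1/1.18 = 15% of the information.

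**Cost of adding block when blocks do not differ.** With 44 subjects the half-width rises from 0.628 to 0.636, or 1.3%. With random loss to the 24 and 12 completers of Protocol 8.5, fixed-block intervals are about 3.4% wider on average (5th to 95th percentile 1.2% to 6.7%), and some block loses an arm in about 14% of simulated trials.

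**Random block intercept.** Under generalised least squares at ICC 0.1, the Block 6 weight falls from 0.089 to 0.049. The bias is reduced but not removed.

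**The case against.** The strongest reply is that the harm depends on something the documents neither state nor quantify. The study is single-site, EtCO2 is measured with standardised equipment under an SOP, and the link from block to dosing subgroup is only inferred from the sizes. This stands: without block effects the planned analysis is unbiased and its interval correct.

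Second, Emax is already a change from predose, and baseline is also a covariate. A constant offset, such as a monitor reading high in one subgroup, cancels before modelling. For Emax, only a block difference in the size of the response can leak in. This stands too. It applies less to the predose averages, which are levels, where only the baseline covariate would absorb such an offset. Because baseline is taken before morphine on Day 1, adjusting for it need not remove subgroup differences in postdose response.

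Third, exposure is narrow. Contrasts 1 and 2 compare Day 15 with Day 1 in the same subjects, so an additive block effect cancels. Contrast 1 is the one that matches the primary objective, and the primary incidence endpoints are only tabulated. And 32 of the 44 subjects sit in 5:3 blocks, close to the overall 7:4.

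A reader might infer that the AZD4041-versus-placebo contrast is confounded with calendar time, or that its interval is too short. The documents do not support either. The association with block is weak, no calendar effect is documented, and the error in the interval runs in the conservative direction.

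**Conclusion.** The point holds as a low-severity omission. The SAP creates an association between block and sequence and then leaves block out of the models. For the two between-sequence contrasts, the consequence is a bias of about 0.09 SD (0.28 SE) per 1 SD shift in Block 6, and a 95% interval that covers about 96% to 97% at a block ICC of 0.2 to 0.3. Both figures rest on assumed block effects and on a one-time-point model without the baseline covariate. Dropout and replacements would change the realised weights. The finding gives no reason to doubt the within-subject contrasts or the incidence tables.

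**What to change.** In SAP 9.1, add randomisation block as a fixed effect in the models that give the between-sequence contrasts (Day 15 Emax and predose averages), or at minimum prespecify that model as a sensitivity analysis. In SAP 3.4, assign each replacement to the block of the subject replaced. State that a block left with only one arm is pooled with its neighbour; Blocks 1 and 6, with two placebo subjects each, are the most likely to need it. A random block intercept is a weaker option because it removes only part of the bias.

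The change is a few lines of text and up to 5 degrees of freedom. The price, if blocks do not differ, is the 1% to 3% widening shown above. If they do differ, the interval narrows: by 8% at ICC 0.20 (0.692 to 0.636). It should be made before database lock, because SAP 5.1 treats analyses added after lock or unblinding as post hoc and exploratory.

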3.5 Determination of Sample Size

No formal sample size calculation was performed for this Phase 1 study.

4 ANALYSIS POPULATIONS

The following populations are defined for this study:

- **Randomized Population:** The randomized population will include all subjects who are randomized to the Treatment phase.
- **Safety population:** The safety population will include all subjects who received at least 1 dose of morphine, placebo, or AZD4041.
- **Completer Population:** The completer population will include all subjects in the safety population who completed the entire Treatment phase and the follow-up period (up to at least Day 22). This population will be used for inferential analysis of maximum postdose

increase in EtCO₂ (E_{max} (postdose – predose)), maximum postdose reduction in SpO₂ (E_{max} (predose – postdose)), and maximum postdose decrease in respiratory rate (E_{max} (predose – postdose)).

- **Pharmacokinetic Population:** All subjects in the safety population who received at least 1 dose of morphine or AZD4041 and have at least 1 PK concentration after dosing will be included in the PK population.

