#### 4.4.2. After First Treatment Administration

Subjects may, at any time, voluntarily withdraw from the study or be removed from the study at the discretion of an Investigator or Sponsor. An Investigator may withdraw a subject at any time for any (but not limited to) of the following reasons: if it is determined that continuing the study would result in a significant safety risk to the subject or if their behavior is deleterious to the study environment. If such withdrawal occurs, or if the subject fails to return for visits, an Investigator should determine the primary reason for a subject's premature withdrawal from the study and record the reason in the subject's study documents.

In the case of a clinically significant illness detected during the trial (including COVID-19 diagnosis), the Principal Investigator (or delegate) will, in consultation with the Medical Monitor and Sponsor Physician, determine the most appropriate course of action on an individual basis. Evaluations will include but are not limited to:

- The safety of the subject and other study participants
- The possible effect the illness would have on the results gathered during the trial, and their ability to be appropriately analyzed or interpreted
- The possibility of suspending participation then re-initiating it after recovery
- The implication of any inclusion or exclusion criteria that would contradict possible actions
- The implication of any adherence to regulatory guidelines that may be affected by actions decided; for example group effect analysis
- The sample size calculation, current number of subjects, and possibility of replacement subjects

Evaluations and decision-making for subject removal will be documented in the study file, reported to the Sponsor, and discussed where appropriate in the Clinical Study Report.

Attempts should be made to have such subjects complete the End of Study/Early Termination assessments. End-of-Study/ET assessments should be performed as soon as possible after the last study treatment administration.

For subjects lost to follow-up (ie, those subjects whose status is unclear because they fail to appear for study visits without stating an intention to withdraw), an Investigator should show "due diligence" by documenting in the source documents steps taken to contact the subject, eg, dates of telephone calls (at least 3), registered letters (at least 1), etc.

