## 6.1.15. Medical Interventions for Signs of Respiratory Depression

In the event that subjects show signs and symptoms of respiratory depression, the Investigator or study staff will begin intervention procedures that may escalate in the degree of intervention as follows:

- Verbal stimuli: Call the subject's name loudly. If no response and/or no improvement in respiratory depression, proceed to physical stimuli.
- Physical stimuli: Apply sternal rub to subject and/or apply nail bed pressure. If subject is unable to be aroused and/or there is no improvement in signs of respiratory depression, proceed to O2 administration and prepare for possible naloxone administration (if there is no improvement with verbal or physical stimuli, there is a high likelihood of requiring naloxone administration).
- O2 administration: Administer oxygen with a target SpO2 of 95-100%. Prepare naloxone for administration if no improvement in respiratory depression clinical parameters or as per Investigator discretion.
- Naloxone administration: Administer naloxone (eg, 4 mg/spray IN every 2-3 minutes; 0.4 mg IV every 2-3 minutes to a maximum of 10 mg) and titrate until adequate oxygenation/ventilation is achieved.

The Investigator or designee will choose the appropriate level of intervention as deemed medically necessary. Subjects who receive intervention will be evaluated to determine if further intervention (eg, hospitalization) is warranted. Subjects who show significant signs of respiratory depression that requires naloxone administration or poses significant safety concerns may be withdrawn from the study at the discretion of the Investigator or designee.

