# 8.1.3. Completer Population

The Completer Population will include all subjects in the Safety Population who complete the entire Treatment phase and the follow-up period (up to at least Day 22). This population will be used for inferential analysis of maximum postdose increase in EtCO2 ( $E_{max}$  (postdose – predose)), maximum postdose reduction in SpO2 ( $E_{max}$  (predose – postdose)), and maximum postdose decrease in respiratory rate ( $E_{max}$  (predose – postdose)).

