# 8.3. Safety

Statistics for summary of AEs and safety results will be detailed in a SAP.

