## 8.3.2. Safety Analysis

#### 8.3.2.1. Respiratory Depression Analysis

Summary statistics and inferential analysis for respiratory depression endpoints will be done using the Completer Population.

Incidence of increased EtCO2 of at least >50 mmHg will be summarized by treatment and time point using frequency tables. Mean time to each increased EtCO2 episode of at least >50 mmHg, mean duration of each increased EtCO2 episode of at least >50 mmHg, and mean postdose EtCO2 will be summarized by treatment and time point using descriptive statistics. Maximum postdose increase in EtCO2  $E_{max}$  (postdose – predose) will be summarized by treatment using descriptive statistics and inferential analysis. EtCO2 averages (predose average from Days 2 to 15), and postdose average on Day 15 will also be summarized by treatment using descriptive statistics and inferential analysis. For each event of significantly increased ETCO2, type of medical intervention used will be listed.

Incidence of reduction in SpO2 to <92% will be summarized by treatment and time point using frequency tables. Mean time to reduction in SpO2 to <92%, mean duration of reduction in SpO2 to <92%, and mean postdose SpO2 will be summarized by treatment and time point using descriptive statistics. Maximum postdose reduction of SpO2  $E_{max}$  (predose – postdose) will be summarized by treatment using descriptive statistics and inferential analysis. SpO2 averages (predose average from Days 2 to 15), and postdose average on Day 15 will also be summarized by treatment using descriptive statistics and inferential analysis. For each event of significantly reduced SpO2, type of medical intervention used will be listed.

Incidence of reduced respiratory rate to <6 breaths/min will be summarized by treatment and time point using frequency tables. Mean time to each reduced respiratory rate episode of < 6 breaths/min, mean duration of each reduced respiratory rate episode of <6 breaths/min, and mean postdose respiratory rate will be summarized by treatment and time point using descriptive statistics. Maximum postdose decrease in respiratory rate  $E_{max}$  (predose – postdose) will be summarized by treatment using descriptive statistics and inferential analysis. Respiratory rate averages

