5 DATA HANDLING AND PRESENTATION

5.1 Safety Analysis Presentation

Adverse events and medical history will be classified using the Medical Dictionary for Regulatory Activities (MedDRA) terminology as defined in the study Data Management Plan (DMP).

Prior and concomitant medications will be coded with the World Health Organization Drug Dictionary (WHODrug) as defined in the study DMP.

In general, all safety summary tables will be presented for the safety population. Summaries for AEs will be presented by treatment and treatment sequence. Summaries for other safety endpoints will be presented by treatment if the endpoints are measured at the end of each period or by treatment sequence if the endpoints are not measured at the end of each period (End of Study only).

In general, the data listings will include all subjects in the safety population up to the point of study completion or discontinuation; exceptions will be listings pertaining to a subset of subjects only (eg, subjects with protocol deviations) or a subset of records/events (eg, abnormal laboratory values). Limited data for those not included in the safety population, eg, who failed screening, may be presented, as appropriate.

Categorical variables will be summarized using sample size (N), number of available data (n), and the percentage of available data (%) for each class. Continuous variables will be summarized using descriptive statistics, including N, n, arithmetic mean (mean), standard deviation (SD), minimum (min), median, and maximum (max).

The following general considerations may be applied:

- Study Day will be derived from the reference date (eg, the day of the first dose of study drug) and date of event as:
Study Day = (date of event – reference date) +1, if event is on or after the reference date;
Study Day = date of event – reference date, if event is before the reference date.
- Duration will be calculated using the general formula: (end date - start date) +1.

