9 SAFETY ANALYSIS

9.1 Respiratory Depression Analysis

Summary statistics and inferential analysis for respiratory depression endpoints will be presented for all subjects who completed all EtCO₂ assessments in addition to the Safety Population, when possible. Incidence of increased EtCO₂ of at least >50 mmHg will be summarized by treatment and time point using frequency tables. Mean time to each increased EtCO₂ episode of at least >50 mmHg, mean duration of each increased EtCO₂ episode of at least >50 mmHg, and mean postdose EtCO₂ will be summarized by treatment and time point using descriptive statistics.

Maximum postdose increase in EtCO₂ E_{max} (postdose – predose) will be summarized by treatment using descriptive statistics and inferential analysis. EtCO₂ averages (predose average from Days 2 to 15), and postdose average on Day 15 will also be summarized by treatment using descriptive statistics and inferential analysis. For each event of significantly increased ETCO₂, type of medical intervention used will be listed.

Incidence of reduction in SpO₂ to <92% will be summarized by treatment and time point using frequency tables. Mean time to reduction in SpO₂ to <92%, mean duration of reduction in SpO₂ to <92%, and mean postdose SpO₂ will be summarized by treatment and time point using descriptive statistics. Maximum postdose reduction of SpO₂ E_{max} (predose – postdose) will be summarized by treatment using descriptive statistics and inferential analysis. SpO₂ averages (predose average from Days 2 to 15), and postdose average on Day 15 will also be summarized by treatment using descriptive statistics and inferential analysis. For each event of significantly reduced SpO₂, type of medical intervention used will be listed.

Incidence of reduced respiratory rate to <6 breaths/min will be summarized by treatment and time point using frequency tables. Mean time to each reduced respiratory rate episode of < 6 breaths/min, mean duration of each reduced respiratory rate episode of <6 breaths/min, and mean postdose respiratory rate will be summarized by treatment and time point using descriptive statistics. Maximum postdose decrease in respiratory rate E_{max} (predose – postdose) will be summarized by treatment using descriptive statistics and inferential analysis. Respiratory rate averages (predose average from Days 2 to 15), and postdose average on Day 15 will also be summarized by treatment using descriptive statistics and inferential analysis.

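### Protocol and SAP name different, unranked sets for the respiratory analyses, and both completion-based sets can lose a subject withdrawn on Day 15 for respiratory depression

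*SAP*

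**What the plan says.** The sets named for the respiratory analyses are:

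- **Protocol 8.1.3** defines completers as Safety Population subjects "who complete the entire Treatment phase and the follow-up period (up to at least Day 22") and assigns them to the inference on maximum change (Emax) in EtCO2, SpO2 and respiratory rate. **SAP 4** does the same, for those "who completed the entire Treatment phase and the follow-up period (up to at least Day 22").
- **Protocol 8.3.2.1** goes further: "Summary statistics and inferential analysis for respiratory depression endpoints will be done using the Completer Population". That covers the frequency tables for the two primary incidences as well as Emax.
- **SAP 9.1**, which specifies these analyses, does not mention completers. Its summaries and inference "will be presented for all subjects who completed all EtCO₂ assessments in addition to the Safety Population, when possible". The all-EtCO2 set does not appear in SAP 4.
- **SAP 5.1** has a general default: "In general, all safety summary tables will be presented for the safety population".
- **Protocol 8.3** defers to the SAP: "Statistics for summary of AEs and safety results will be detailed in a SAP".

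Two further provisions decide who can drop out of these sets. Protocol 6.1.15 states: "Subjects who show significant signs of respiratory depression that requires naloxone administration or poses significant safety concerns may be withdrawn from the study", at the investigator's discretion. Protocol 4.4.2 states: "End-of-Study/ET assessments should be performed as soon as possible after the last study treatment administration".

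**The concern.** The trial asks whether AZD4041 worsens the respiratory effect of morphine. Two things are at stake.

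First, the result reported as the main one could come from any of three sets, and nothing fixed before unblinding says which. Deferring to the SAP does not settle this, because SAP 4 and SAP 9.1 disagree on the same Emax inference. The SAP cites protocol version 1.0, but the Amendment 01 summary lists only morphine supply details and the day in exclusion criterion 23, so the version gap does not explain the difference.

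Second, membership of two of the sets is decided after dosing, by events linked to the outcome. A subject with severe respiratory depression on Day 15 is the one most likely to be withdrawn, and is also the one the comparison most needs. If AZD4041 did worsen respiratory depression, more such subjects could be lost from that arm, and the estimated harm would shrink.

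**Working it through.** **1. When a subject leaves each set.** Protocol Table 6-10 puts the last EtCO2 reading 24 hours after the Day 15 dose. Completers need follow-up to Day 22.

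| Subject | All-EtCO2 set | Completers | Safety Population |
|---|---|---|---|
| Naloxone on Day 15, stays, all readings, followed up | in | in | in |
| Withdrawn on Day 15 before 24 h, early-termination visit only | out | out | in |
| Misses one EtCO2 reading, followed up | out (literal reading) | in | in |
| All readings done, no follow-up | in | out | in |

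The last two rows show that neither completion-based set contains the other. A withdrawal after Day 1 morphine but before Day 2 precedes AZD4041 or placebo, so randomised treatment cannot cause it.

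**2. What the all-EtCO2 rule requires.** Readings per subject from Table 6-10: Day 1, 6 + 10 = 16; Days 2-7, 6; Day 8, 1 + 10 = 11; Days 9-14, 6; Day 15, 1 + 11 = 12. The total is 51. Of these, 6 + 11 + 6 = 23 fall on Days 2-14 and play no part in the Day 1 and Day 15 Emax contrasts. Read literally, missing any one of the 51 also removes the subject's SpO2 and respiratory-rate data.

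How many qualify depends on how readings go missing, which the documents do not say:
- Independent, 0.2%, 0.5% or 1% missing: 0.998^51, 0.995^51, 0.99^51 = 90%, 77%, 60%.
- Clustered in early leavers who each lose 12 to 25 readings: 51 × 0.002 = 0.10 to 51 × 0.01 = 0.51 readings missing per subject on average. Leavers are then 0.10/25 = 0.4% to 0.51/12 = 4.3% of subjects, so about 96% to 99.6% qualify.

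**3. Dilution of EtCO2 Emax on Day 15.** Arm sizes 28 and 16 are from protocol 8.5. Assumed: normal Emax, means 11 and 8 mmHg, SD 5, and subjects above 15 leave with probability q.
- SE = 5 × √(1/28 + 1/16) = 1.57 mmHg.
- P(above 15) = P(Z > 0.8) = 0.212 on AZD4041 and P(Z > 1.4) = 0.081 on placebo.
- Mean below and above 15: 9.16 and 17.84 (AZD4041); 7.19 and 17.27 (placebo).
- Retained mean = [(1 − p) × mean below + (1 − q) × p × mean above] / (1 − q × p), where p = P(above 15).

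| q | Expected difference (mmHg) | Shift / SE |
|---|---|---|
| 0 | 3.00 | 0 |
| 0.10 | 2.93 | 0.05 |
| 0.25 | 2.81 | 0.12 |
| 0.50 | 2.58 | 0.27 |
| 1.00 | 1.98 | 0.65 |

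The last row is extreme: it loses 28 × 0.212 = 5.9 AZD4041 subjects, more than the 28 − 24 = 4 that the completer target allows for.

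**4. Primary incidence on Day 15.** Assumed: 8/28 against 3/16 responders.
- No loss: 28.6% − 18.8% = 9.8 points, SE = √(0.286 × 0.714/28 + 0.1875 × 0.8125/16) = 13.0 points.
- 2 and 1 responders leave: 6/26 − 2/15 = 9.7.
- 1 leaves AZD4041 only: 7/27 − 3/16 = 7.2.
- 2 leave AZD4041 only: 6/26 − 3/16 = 4.3.

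**5. Follow-up window.** Protocol 3.1 sets follow-up at 7 ± 2 days after the last dose: Day 15 + 5 to Day 15 + 9 = Days 20 to 24. A compliant visit on Day 20 or 21 does not literally reach Day 22.

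**The case against.** The route to loss is narrow. Day 15 is the last dose, so withdrawal then stops no further treatment. Subjects stay confined to Day 18, respiratory monitoring is extended if medically needed, and withdrawal after naloxone is discretionary. All of this stands. A reader might infer that every naloxone-treated subject leaves the analysis. The documents do not say so: a subject who stays and is followed up remains a completer.

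SAP 9.1 also plans Safety Population output, which keeps a Day 15 withdrawal, and its qualifier can be read as meaning where data exist. This stands in part. The output is planned, but it is neither guaranteed nor named as primary, and SAP 5.1's default is general and concerns summary tables, not inference.

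A reader might also infer from section 2 of the working that the all-EtCO2 rule discards up to 40% of subjects, or that the choice of set often changes the conclusion. The documents do not support either. Independent missingness is a strong assumption for confined inpatients, and under clustering nearly everyone qualifies.

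SAP 9.1 calls respiratory-rate Emax the primary criterion, whereas the illustration uses EtCO2. The shift in SE units depends only on the standardised inputs (difference 3/5 = 0.6 SD, cuts at 0.8 and 1.4 SD), so it applies to any parameter with those values; the mmHg figures do not.

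Finally, Day 22 may simply be the nominal name of a visit scheduled with a ± 2 day window. That is a fair reading, and the point affects precision only.

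**Conclusion.** The conflict is in the text. Three sets are named for the respiratory analyses, SAP 4 and SAP 9.1 disagree on the Emax inference, and none is ranked. Two of the sets can lose a subject because of respiratory depression on Day 15, in a direction that hides harm.

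The size is unknown and probably small. With 10% to 50% of high responders lost, the EtCO2 Emax shift is 0.05 to 0.27 SE. The incidence difference barely moves under similar loss in both arms and falls further only if the loss is one-sided. Even the fall from 9.8 to 4.3 points (5.5 points) is well inside the SE of 13.0. Event rates, means, SD and loss probabilities are all assumptions. The primary incidences are planned as frequency tables, so for them the effect is on a descriptive comparison.

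The documents do not show that the plan will conceal a respiratory effect. They leave the choice of set open, and two of the available choices can select on outcome. This should be fixed before unblinding, because a choice made afterwards would be post hoc under SAP 5.1.

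**What to change.** Before unblinding, name one primary respiratory set, worded identically in protocol 8.1.3 and 8.3.2.1 and in SAP 4 and 9.1: all randomised subjects who received morphine on the day analysed. Remove the follow-up condition, the all-EtCO2 condition and the qualifier on the Safety Population from that set.

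- **Emax and averages:** include each subject with at least one postdose value of that parameter on that day, and use all available data in the planned mixed model. No imputation is needed, so SAP 5.2 is respected. The Days 2-15 predose average needs its own line, since no postdose value enters it.
- **Incidences:** use all subjects given morphine that day as the denominator, count any qualifying episode before withdrawal as an event, and report how many subjects without an event had incomplete monitoring.
- **Sensitivity:** keep completers, counting any follow-up visit on Days 20 to 24 as complete.
- **Reporting:** show the number of readings behind each Emax.

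The cost is a few lines in each document, and the protocol change goes to the IRB under protocol 12.2. The downside is that a truncated series can understate both Emax and incidence, so the completer result should be read beside the primary one. No change to patient care is proposed.
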